## 3.2 Sample Size

This is an exploratory trial and the sample-size is not based on formal statistical considerations. The numbers assigned to each treatment group are considered adequate to describe the tolerability, safety and pharmacokinetics.

Assuming that an event occurs in 10% of the cases, the probability to see at least one case in 16 subjects on combination treatment is 81%. If the event occurs in 20% of the cases, this probability increases to 97%.

Participants recruitment has stopped at 37.

## 3.3 Randomisation and Blinding

### Subject Randomisation

All subjects in this trial will be assigned to a treatment regimen according to a randomisation schedule generated by a statistician using PROC Plan. Details regarding the unique screening and subject number will be included in the SOM.

Eligible subjects will be randomly assigned in a 2:1:1:1 ratio to one of four treatment arms on Day 1, at the point of dosing. Treatment arms are outlined below:

- Treatment 1 (N=16): PYR + PQP
- Treatment 2 (N=8): PYR + placebo for PQP
- Treatment 3 (N=8): placebo for PYR + PQP
- Treatment 4 (N=8): placebo for PYR + placebo for PQP.

Sentinel dosing (N=10) will occur: four subjects for treatment arm 1, and two subjects from each of treatment arms 2, 3 and 4, will be dosed before the remaining subjects of each treatment arm are dosed together (see protocol Section **Error! Reference source not found.**).

## Methods for ensuring blinding

The trial will take place in a double-blind fashion whereby subjects and clinical trial site staff are blinded to the active or placebo trial drug assignment.

PQP is uncoated and bitter to taste, the effect may be persistent for some time after administration. This effect cannot be masked and may provide an indication of the treatment received. As the key safety and tolerability endpoints are objective assessments and parameters, it is anticipated that there will be no impact on the primary trial objective to determine the safety and tolerability of the registered doses of IMP.

The pharmacy staff preparing the investigational products will not be blinded to trial drug assignment. During the trial, the individual randomisation codes will be kept in the site's clinical trials pharmacy, accessible to the pharmacy personnel only. Upon completion of the trial, after the database lock and after the blind is revealed, the randomisation list will be filed in the Trial Master File (TMF).

Sponsor staff involved in clinical decision-making (such as those involved in SRC decisions) will be blinded to trial drug assignment.

## **4. STATISTICAL ANALYSES**

### **4.1 General Notes for Statistical Analyses**

In general, descriptive statistics for continuous variables will include number of non-missing values (n), arithmetic mean, standard deviation (SD), median, minimum, and maximum.

Descriptive statistics for PK parameters will include N - the number of participants, n - the number of samples, n(LLOQ) - the number of samples <LLOQ (lower limit of quantification), arithmetic mean, SD - standard deviation, CV - coefficient of variation, geometric mean, median, minimum, maximum.

Categorical variables will be summarized using frequency counts and percentages.

For all tables, except PK parameter tables, descriptive statistics for minimum and maximum will be presented with the same decimal digits as the original data, and with 1 more decimal place than the original data for mean and median; SD and SE will be reported with 2 more decimal places than the original data. Degrees of freedom based on the Kenward Roger approximation will be presented with one decimal.

PK parameters will be presented as follows in the listing:  $C_{\max}$  and  $t_{\max}$  will be presented as given in the raw data; other PK parameters will be presented with 3 decimal places. Descriptive statistics for PK parameters will be presented with decimal places as appropriate for the particular parameter and treatment group.

The analyses will be presented by treatment group (2 monotherapies, combination therapy and placebo), overall as well as stratified by body weight group:

- < 65 kg
- 65 - < 75 kg
- $\geq$  75 kg.

- Treatment arm 1:
  - PYR 540 mg + PQP 960 mg
  - PYR 720 mg + PQP 960 mg
  - PYR 720 mg + PQP 1280 mg
- Treatment arm 2
  - PYR 540 mg
  - PYR 720 mg
- Treatment arm 3
  - PQP 960 mg
  - PQP 1280 mg
- Overall (for safety set)
- Placebo

All collected data will be presented in by-subject listings. Listings will be ordered by treatment group, body-weight group and subject number and will include all randomized subjects.

Unless otherwise stated, baseline will be defined as the last non-missing value prior to first administration of study drug. Changes from baseline values will be calculated as the post-baseline assessment value minus the baseline value. Only observed values from scheduled time points will be used to create summary tables.

Deviations from the planned analyses will be described in the final clinical study report (CSR).

Page layout of the TFLs will be in landscape mode and will be provided as individual RTF format. Further details of page layout will be provided in the TFL shell document.

If repeated measurements are made at a time point, the first scheduled value will be used for summary analysis, unless otherwise stated in relevant section of this SAP.

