### 4.11.2 Laboratory Data

Clinical laboratory parameters (including blood chemistry, haematology, coagulation, urinalysis and other laboratory results) will be listed and abnormal parameters will be flagged and graded as high (H/x) or low (L/x) (where defined) according to reference ranges and CTCAE grade. Absolute (observed) values and changes from baseline (continuous variables) will be summarized for each parameter and scheduled time point by treatment group. The number of volunteers presenting out-of-range and clinically relevant values will be summarised by treatment group. The scheduled lab value will be used for summary analysis if repeated measurements are made at any time point.

For summary statistics, a lab value with "<" will be replaced with a numeric value by removing the "<" sign. In the listings, the values will be displayed as originally reported by the laboratory.

The mean and individual change from baseline value of ALT/AST/Bilirubin will be plotted by treatment group and by time-point. The number of subjects presenting out-of-range and clinically relevant values will be summarised.

The qualitative urinalysis data will be listed only.

Test Code	Test Unit	Range Low	Range High	Grade 1	Grade 2	Grade 3	Grade 4
ALT	IU/L	10	50	>ULN - 3.0 x ULN	>3.0 - 5.0 x ULN	>5.0 - 20.0 x ULN	>20.0 x ULN

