## 4.11.3 Vital Signs

Vital signs data (SBP, DBP, Pulse rate, temperature) will be listed for individual subjects. Summary statistics of absolute (observed) values and changes from baseline will be calculated for each parameter and scheduled timepoint by treatment group.

Out-of-reference-range values will be flagged as high (H) or low (L) and as being clinically relevant or not: the number of subjects presenting out-of-range and clinically relevant values will be summarised.

Parameter	Normal Range
Temperature (tympanic)	35-37.5°C
Systolic Blood Pressure (Supine)	90-140 mmHg
Diastolic Blood Pressure (Supine)	40-90 mmHg
Postural Drop (systolic, symptomatic)	≤20 mmHg drop
Pulse Rate (supine)	40-100 bpm
Respiratory Rate	8-20 breaths per min

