## 4.11.4 Telemetry and Holter

Cardiac telemetry and Holter data (Start / End Date time and evaluation) will be listed by subject.

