# Statistical Analysis Plan

All un-adjudicated ECG data (PR, QRS, QT, QTcB, QTcF and HR) including H/L flags and overall ECG evaluation will be listed. Out-of-reference-range values will be flagged as clinically relevant or not. Reference ranges for ECGs are as follows:

Parameter	Normal Range
Heart Rate (Supine)	40-100 bpm
PR Interval	120-220 ms
QRS duration	≤120 ms
QTcF	≤450 ms (Males & Females)

For summary statistics an arithmetic mean value, of the last 3 evaluable ECGs of each timepoint, will be used at each time-point. All below analyses will be performed using this set.

ECG data and changes from baseline will be summarised using descriptive statistics.

The change from baseline will be derived using the arithmetic mean value of each time-point triplicate minus baseline value, where baseline is the arithmetic mean of the pre-dose QTcF values of Day 1.

Furthermore, categorical analysis of QTcF data will be presented as follows:

- Absolute QTcF interval prolongation
  - QTcF interval > 450 ms to ≤ 480 ms
  - QTcF interval > 480 ms to ≤ 500 ms
  - QTcF interval > 500 ms
- Change from baseline in QTcF interval
  - QTcF interval increases from baseline > 30 msec to ≤ 60 msec
  - QTcF interval increases from baseline > 60 ms

The mean change from baseline value of QTcF will be plotted by treatment group and by time-point. The number of subjects presenting out-of-range and clinically relevant values will be summarised.

Additional categorical analysis will be presented as follows:

- increase of PR from baseline >25% resulting in PR > 200 ms
- increase of QRS from baseline >25% resulting in QRS > 120 ms
- decrease of HR from baseline >25% resulting in HR < 50 bpm
- increase of HR from baseline >25% resulting in HR > 100 bpm.

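### SAP 4.1's scheduled-only rule has no stated exception for participant counts, so a clinically relevant value or higher ECG category found only off-schedule can be left out of the tables behind the primary proportions

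*SAP*

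**What the plan says.** SAP 4.1 (General Notes) sets the rule for all output: "Only observed values from scheduled time points will be used to create summary tables". The same section presents categorical variables as counts and percentages, so a count of participants is itself summary output. For repeats at a time point, "the first scheduled value will be used for summary analysis, unless otherwise stated in relevant section of this SAP". The closing clause there qualifies the repeat rule, not the scheduled-only sentence.

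The affected counts are set out in three places:

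- **Laboratory, SAP 4.11.2:** "The number of volunteers presenting out-of-range and clinically relevant values will be summarised by treatment group". The next sentence is the laboratory repeat rule: "The scheduled lab value will be used for summary analysis if repeated measurements are made at any time point".
- **Vital signs, SAP 4.11.3:** "the number of subjects presenting out-of-range and clinically relevant values will be summarised".
- **ECG, SAP 4.11.6:** "For summary statistics an arithmetic mean value, of the last 3 evaluable ECGs of each timepoint, will be used at each time-point". The section then ties all analyses that follow to that set. These include the QTcF, PR, QRS and HR categories and the count of clinically relevant values.

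The primary endpoints in SAP 2.2 and Protocol 2.2.1 are proportions of participants with clinically significant changes. They carry no limit to scheduled visits.

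**The concern.** The protocol expects safety values outside the schedule. Table 7 lets the investigator order extra assessments for one participant (feature 7) and allows ECGs paired with PK samples after QT or LFT changes (feature 14). Protocol 7.9.2 allows extra recordings after an abnormal ECG. Such tests are ordered because something looks wrong, so they are a likely place for a clinically relevant value to turn up.

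If the scheduled-only rule governs the participant counts, a value found only on such a test is in the listing but not in the table. The omission can only lower the count. With 8 or 16 planned per arm, one such case can be the difference between none and one. Two programmers could also reach different primary counts from the same data, depending on how far each takes the rule to reach.

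**Working it through.** **1. The plan's own figure.** SAP 3.2 gives the chance of at least one case among 16 combination participants. The formula is 1 − (1 − p)^n.
- p = 0.10: 1 − 0.9^16 = 0.815 (stated 81%)
- p = 0.20: 1 − 0.8^16 = 0.972 (stated 97%)

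Both reproduce and neither is disputed.

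**2. How far the rule reaches, section by section.**

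| Count | Where scheduled time points are mentioned | Off-schedule values admitted? |
|---|---|---|
| Laboratory (SAP 4.11.2) | In the descriptive-statistics sentence; the repeat rule after the count keeps the scheduled value | Not stated; SAP 4.1 governs by default |
| Vital signs (SAP 4.11.3) | In the descriptive-statistics sentence only | Not stated; SAP 4.1 governs by default |
| ECG intervals and categories (SAP 4.11.6) | Timepoint means, with all later analyses tied to them | No. A repeat at a scheduled time point can enter through the last-three rule; an ECG between time points cannot |

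**3. Outputs not affected.** SAP 4.11.2 says "The qualitative urinalysis data will be listed only". SAP 4.11.4 says "Cardiac telemetry and Holter data (Start / End Date time and evaluation) will be listed by subject". The overall ECG evaluation is also listed only. None of these has a count that could lose a case.

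**4. An example from the protocol's dates.** Protocol 1.2.2.2 puts the peak of pyronaridine ALT/AST elevations 8 to 15 days after the first treatment day. Counting from Day 1, that is Day 9 to Day 16. Table 5 schedules bloods from Day 8 on at Days 8, 15, 22 and 30.
- Intervals: 15 − 8 = 7, 22 − 15 = 7 and 30 − 22 = 8 days.
- Days 9 to 14 have no scheduled test: 14 − 9 + 1 = 6 days. If the window is read as Days 8 to 15, the same 6 days are empty.

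Suppose ALT is raised on Days 8 and 15 but judged not clinically relevant, and an extra test between them is judged clinically relevant. The literal rule counts the participant as out of range but not as clinically relevant, and the second is the primary quantity.

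**5. Size per affected participant.** 1/16 = 6.25 points (combination) and 1/8 = 12.5 points (each other arm), for planned arms. SAP 3.2 says recruitment stopped at 37, which is 40 − 37 = 3 short, and does not give the arm sizes. If all three were missing from one arm, the step would be 1/13 = 7.7 or 1/5 = 20 points.

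**6. Illustration under an assumption.** Let f be the share of participants with a clinically relevant value whose value is found only off-schedule. The documents do not give f; 10%, 25% and 50% are assumed. The chance of at least one counted case is 1 − (1 − p(1 − f))^n.

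| n, p | All values counted | f = 10% | f = 25% | f = 50% |
|---|---|---|---|---|
| 16, 10% | 81.5% | 77.9% | 71.3% | 56.0% |
| 16, 20% | 97.2% | 95.8% | 92.6% | 81.5% |
| 8, 10% | 57.0% | 53.0% | 46.4% | 33.7% |

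The table shows the direction and range only; it is not an estimate.

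**The case against.** The strongest reply is that the rule was never meant to reach participant counts. The sentence closes a paragraph on baseline and change from baseline. SAP 4.11.2 and 4.11.3 attach the scheduled time point to the descriptive statistics and then give the count without it. Taken to the letter, the rule would also reach the TEAE and concomitant-medication tables, which have no scheduled time points. This stands in part: for laboratory and vital signs a by-timepoint reading is open. It does not help for ECG, where SAP 4.11.6 ties the counts to timepoint means, and nowhere does the SAP state the narrower scope.

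Second, important values reach a primary table another way. Protocol 8.1 makes an abnormal result an AE if it comes with symptoms or needs further testing or intervention. Protocol 8.2.5 names ALT or AST above 3 × ULN, uncorrected QT above 500 ms and the haemoglobin and platelet drops as events of special interest. This also stands in part. Protocol 8.3 limits double recording of findings captured by other methods, and TEAE incidence is a separate primary endpoint from these proportions.

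Third, the liver example needs a particular sequence of results, and a participant whose scheduled value prompted the extra test is already counted as out of range. Both are true, which is why the gap is narrow.

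Fourth, counting discretionary tests may favour the arm tested less. That is a fair cost, and it is why the scheduled-only count should also be shown.

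**Conclusion.** The point holds as a narrow one that should be fixed. As written, explicitly for ECG and through the general rule for laboratory and vital signs, a participant whose only clinically relevant value or higher ECG category comes from an individual off-schedule or repeat assessment can be left out of the counts behind the primary proportions. The step is 6.25 or 12.5 points per participant in a planned arm. It is not an expected effect, and the number affected cannot be derived. The verdict assumes that the SAP's clinical-relevance flag is how the endpoint's clinical significance is measured.

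A reader might infer more than the documents support:

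- **That off-schedule values are lost.** They are not: SAP 4.1 lists all collected data, and many such values may also be TEAEs.
- **That early-termination data are dropped.** SAP 4.3 includes withdrawn participants up to discontinuation, and Protocol 5.6.1 uses the last-visit procedures. Only the visit label is unstated.
- **That every added assessment is off-schedule.** Those under Table 7 feature 8 are put into the schedule for upcoming participants.
- **That the SAP contradicts the protocol.** Protocol 10.3 is silent on off-schedule values.
- **That the sentinel decision is affected.** Under Protocol Table 8 the safety committee reviews all available safety data, not these tables.

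**What to change.** 1. In SAP 4.1, state that the scheduled-only and repeat rules apply to by-timepoint descriptive statistics and plots.
2. In SAP 4.11.2, 4.11.3 and 4.11.6, state that a participant counts as out of range, or as clinically relevant, if any post-dose value carries that flag, whether scheduled, repeat, unscheduled or early termination. The rule should be any flagged value rather than one worst value per parameter. Clinical relevance is judged separately from high or low, so the extreme value need not be the flagged one.
3. For the numeric QTcF, PR, QRS and HR categories, use the most extreme post-dose value in the direction of the category. Restrict it to recordings comparable with Protocol 7.9.1 (resting, supine, 12-lead), so 5-lead and Holter recordings do not enter.
4. State how the early-termination visit is labelled.
5. Show the scheduled-only count beside the all-values count.

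The cost is wording in four SAP sections, a participant-level flag, one derived extreme per ECG category and one extra column. Some counts will look less favourable, and participants tested more often have more chances to be counted; the scheduled-only column makes that visible. No visit, dose or clinical rule changes. Protocol 10.1 requires sign-off of the SAP before database hard lock, so the wording should be settled by then.

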## 4.2 Interim Analysis

No interim analysis is planned for this study.

## 4.3 Analysis Sets

The analysis of data will be based different analysis sets according to the purpose of analysis. Subject eligibility for each analysis set will be finalised before the

database hard lock. A subject who withdraws prior to the last planned observation in a tail period will be included in analyses up to the time of discontinuation.

The following data sets will be used for analysis and presentation of the study data:

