#### **1.2.2.2 Pyronaridine (PYR)**

Transient ALT/AST elevations above 3 x ULN are commonly reported in clinical trials investigating the three-day regimen of PYR-AS (pyronaridine-artesunate, Pyramax®). These elevations have been reported in both patients treated for acute uncomplicated malaria and healthy participants enrolled in clinical pharmacology studies. The overall pattern seems consistent across studies with a transient asymptomatic elevation in ALT/AST without bilirubin elevation which for most of the episodes occurred after the three-day treatment, within three and seven days after the initial dose and resolved within 21 days after reaching a peak value between eight and fifteen days after the first day of treatment. Higher elevations of >10 x ULN in patients and >5 x ULN in healthy have also been reported but are less common.

Concomitant elevation in bilirubin and possible Hy's Law cases have not been reported in healthy participants. In a retrospective pooled analysis of completed trials in patients, a total of 16 cases defined as concomitant elevations in ALT or AST >3 x ULN and total bilirubin >2xULN (i.e. Hy's Law cases) were reported in the clinical development program for PYR-AS. Ten cases were reported in malaria patients receiving PYR-AS and six were also reported in patients receiving one of the comparator malaria drugs which could possibly suggest a confounding background effect of the disease. Of these 16 cases, the Independent Safety

---

Monitoring Board adjudicated six possible Hy's Law cases in the PYR-AS group and four in the comparator drugs group.

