**Table 9: Individual rules (decision 1)**

Adverse Events Related to Trial Drug	Actiona
Moderate (Table 14) except QT interval prolongation, haematology, and liver function, for which rules are specified below)	Trial drug administration may be continued, delayed, temporarily suspended or discontinued in accordance with Investigator's clinical judgment
Moderate LFT increases: ALT or AST value $>3 \times$ and $<5 \times$ ULN	
QT interval prolongation: A prolongation of the uncorrected QT interval of greater than 500 ms, using consistent, technically valid triplicate ECG	Trial drug administration will be discontinued.
Haematology: a) Hb drop of $>25\%$ from baseline on Day-1 (only for values below the laboratory reference range), or to an absolute value of $<100\text{ g/L}$ b) Platelet count drop of $> 25\%$ from baseline on Day-1 (only for values outside the laboratory reference range), or absolute value of $<80 \times 10^9/\text{L}$ c) Clinically significant neutrophil drop b	
Severe (Table 14) except liver function, for which rules are specified below.	
ALT or AST value $>3 \times$ and $<5 \times$ ULN, and symptomatic or ALT or AST value $>5 \times$ ULN +/- symptoms b	
Serious (fatal or life-threatening)	
Serious LFT increase: ALT or AST value $>3 \times$ ULN together with bilirubin $>1.5 \times$ ULN, without other evidence of cholestasis	

aActions are only relevant for dosing regimens where additional doses are planned for administration.

bSymptoms include fatigue, nausea, vomiting, right upper quadrant pain or tenderness, fever, rash and/or eosinophilia (eosinophil percent or count above the ULN). Abbreviations: ALT: alanine aminotransferase; AST: aspartate aminotransferase; ECG: Electrocardiogram; Hb: Haemoglobin; ms: milliseconds; QT: QT interval; ULN: upper limit of normal.

\*Investigator judgement will be used to determine which of the pre-dose measurements are considered the baseline. Where possible, the baseline value should be the one that was taken at the closest time of day to the samples being assessed for change, to account for diurnal variation (for example, the D-1 morning blood samples)

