## 5.6 Criteria for withdrawal

The Investigator or designee may withdraw a participant from the trial if the participant:

- is in violation of the protocol, which may jeopardise the trial results or represent a risk to the participant
- has an AE warranting withdrawal
- becomes pregnant
- meets individual rules criteria
- use of/need for a prohibited medication which in the opinion of the Sponsor or Investigator may jeopardise the trial results or represent a risk to the participant
- requests to be withdrawn from the trial (participant withdrawal of consent)
- is found to be considerably non-compliant with the protocol-required dosing visits
- in the Investigator's opinion, is unable to continue trial participation
- is withdrawn from the trial upon the request of Sponsor or the SRC, including if the Sponsor terminates the trial.

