### 5.6.1 Handling of withdrawals

If a participant withdraws or is withdrawn from the trial, the Investigator will inform the Sponsor immediately. If there is a medical reason for withdrawal, the participant will remain under the supervision of the Investigator for protocol-specified safety follow up procedures.

Should any of the participants be withdrawn from the trial (by the Investigator and/or Sponsor) after being dosed, all the relevant assessments in relation to last dose should be completed as per protocol.

Should a participant withdraw themselves from the trial, every effort should be made to conduct a complete Early Termination (ET) visit at an appropriate time-point. The procedures required for the 'last visit' should be performed at this visit.

A participant who fails to return for final evaluations will be contacted by the site in an attempt to have the participant comply with the protocol, in accordance with the site SOPs.

---

When a participant withdraws from the trial, the primary reason for discontinuation must be recorded in the appropriate section of the Case Report Form (CRF).

[figure not shown]

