### **10.2 Analysis sets**

The analysis of data will be based on different analysis sets according to the purpose of analysis. Participant eligibility for each analysis set will be finalised before the database hard lock. A participant who withdraws prior to the last planned observation in a trial period will be included in the analyses up to the time of discontinuation.

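### The analysis rule stops a withdrawn participant's data at discontinuation, so safety follow-up that Protocol 5.6.1 requires can be left out of the safety summaries

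*SAP*

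**What the plan says.** SAP 4.3, in the text that governs all the analysis sets, states that a subject who withdraws before the last planned observation "will be included in analyses up to the time of discontinuation". Protocol 10.2 says the same: such a participant "will be included in the analyses up to the time of discontinuation". Neither place defines the term.

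Protocol 5.6 lists reasons for which the investigator may withdraw a participant from the trial. They include an adverse event that warrants it, and that the participant "meets individual rules criteria". Protocol 5.6.1 then keeps data collection going. If the investigator or sponsor withdraws a dosed participant, "all the relevant assessments in relation to last dose should be completed as per protocol". If the reason is medical, "the participant will remain under the supervision of the Investigator for protocol-specified safety follow up procedures". A participant who leaves by choice should, where possible, attend an Early Termination visit with the last-visit procedures.

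Other parts of the SAP bear on this:

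- SAP 4.1 lists everything collected, but builds summary tables only from values observed at scheduled time points.
- SAP 4.11 runs the safety analyses on the safety set (SAP 4.3: everyone randomised and dosed) and makes no exception to the cut.
- SAP 4.11.1 counts as treatment-emergent any adverse event that starts after dosing begins, with no end date, and lists all adverse events.

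**The concern.** The primary endpoints are incidences and proportions of participants: treatment-emergent events, and clinically significant laboratory, ECG and vital-sign changes. They come from the summary tables, not the listings. With no formal testing planned (SAP 4.11), those tables carry the safety conclusion.

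A cut at withdrawal would leave out data that the trial has gone to the trouble of collecting, in participants some of whom left because of an adverse event. The timing matters for pyronaridine. Protocol 1.2.2.2 says that most ALT/AST elevations "occurred after the three-day treatment, within three and seven days after the initial dose", and that they "resolved within 21 days after reaching a peak value between eight and fifteen days after the first day of treatment". Follow-up after an early withdrawal is when that pattern would show.

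There is also a plain conflict of instructions. The SAP 4.3 cut excludes an event that begins after withdrawal; the SAP 4.11.1 definition includes it. Two programmers working from the same SAP could produce different event counts.

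**Working it through.** **1. What discontinuation means in these documents.** Protocol 5.6.1 uses the word for the reason, recorded on the CRF, why a participant left the trial. SAP 4.4 uses it for subjects who did not complete the study. Table 9 uses it for dosing: "Trial drug administration will be discontinued". The cut in SAP 4.3 applies to a subject who withdraws, which fits the first two uses. The assessments required by 5.6.1 come after that event, so on this reading they fall outside the analysis.

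**2. Timing.** Take a participant withdrawn from the trial on Day 2 or 3.

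- Peak read as Days 8 to 15: shortest gap 8 − 3 = 5 days, longest 15 − 2 = 13 days.
- Peak counted strictly from Day 1 (Days 9 to 16): 9 − 3 = 6 days to 16 − 2 = 14 days.

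Either way the cut precedes the expected peak. In Protocol Table 5 the biochemistry samples after Day 3 fall on Days 4 to 8 (Day 7 for the sentinel group), 15, 22 and 30, and all of these would be outside the summaries.

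**3. Size per uncounted case.** The safety set keeps the participant in the denominator, so one missed case removes one from the numerator.

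- Planned arm of 8: 1/8 = 12.5 percentage points.
- Planned arm of 16: 1/16 = 6.25 percentage points.

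For scale, Protocol 1.2.2.2 reports ALT elevations of 3% (3 to 5 × ULN) and 10% (above 5 × ULN) in Caucasian participants given pyronaridine-artesunate alone, so 3% + 10% = 13% above 3 × ULN. Applying that rate here is an assumption. Expected cases are 0.13 × 8 = 1.04 and 0.13 × 16 = 2.08. One missed case could empty an arm of 8; in the combination arm it would take about 2/16 (12.5%) to 1/16 (6.25%).

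**4. Effect on detection.** The plan's own figures (Protocol 10.7, SAP 3.2) reproduce with P(at least one) = 1 − (1 − p)^n:

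- p = 0.10, n = 16: 1 − 0.9^16 = 81.5% (stated 81%).
- p = 0.20, n = 16: 1 − 0.8^16 = 97.2% (stated 97%).

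Now suppose that k of the 16 are cut before the liver window, so that n = 16 − k can contribute. The documents give no withdrawal rate, so k is an assumption.

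| p | k = 0 | k = 1 | k = 2 | k = 3 |
|---|---|---|---|---|
| 10% | 81.5% | 79.4% | 77.1% | 74.6% |
| 13% | 89.2% | 87.6% | 85.8% | 83.6% |
| 20% | 97.2% | 96.5% | 95.6% | 94.5% |

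For all 24 planned pyronaridine-exposed participants at 13%, the figures are 96.5%, 95.9%, 95.3% and 94.6%. The chance of seeing at least one case falls only slowly. This calculation treats the cut as unrelated to liver risk. The larger exposure is the observed proportion in step 3, because withdrawal may be linked to toxicity.

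**The case against.** Several stronger readings are tempting, and the documents do not support them.

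- **That the data are discarded.** They are not. SAP 4.1 lists all collected data and SAP 4.11.1 lists all adverse events. Only the summaries and, depending on which rule is followed, the event counts are at risk.
- **That everyone stopped early for toxicity is affected.** Table 9 stops the drug, and Protocol 5.6 says only that the investigator may withdraw such a participant. Someone off drug but still in the trial is not clearly within the SAP 4.3 sentence.
- **That the abnormality causing withdrawal is lost.** An ALT or QT value that triggers withdrawal precedes the cut and is counted. Only later developments could be missed. Most liver elevations are also expected after the third dose, so few dosing stops would be for the liver signal itself. The damaging sequence is withdrawal from the trial for another reason followed by a liver rise, or a later withdrawal followed by a higher peak.
- **That one case removes an arm's whole signal.** On the borrowed 13% this could happen in an arm of 8. In the combination arm it halves the expected count.
- **That the loss falls mainly on the active arms and biases towards safety.** This is plausible, but no figure in the documents establishes it.

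The best defence of the wording is that the sentence was meant to keep early leavers in the sets, with discontinuation marking the end of observation; on that reading nothing collected under 5.6.1 is lost. It is a possible intention. It does not match the use of the word in Protocol 5.6.1 and SAP 4.4, and the SAP does not state it. The trial is also exploratory and its safety analysis descriptive, which limits the consequence but leaves the two rules in conflict.

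**Conclusion.** The concern holds in limited form. Followed as written, SAP 4.3 and Protocol 10.2 leave out of the laboratory, vital-sign and ECG summaries the follow-up that Protocol 5.6.1 requires after withdrawal from the trial, and they contradict the treatment-emergent definition in SAP 4.11.1. Later ALT/AST peaks, bilirubin rises, worst severities and late adverse events in withdrawn participants could go uncounted, while remaining visible in the listings.

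The size is 12.5 points per uncounted case in an arm of 8 and 6.25 points in the arm of 16. These use the planned arm sizes: SAP 3.2 reports that recruitment stopped at 37 and does not give the arms. How many cases, if any, would be affected cannot be derived, because no withdrawal rate is given. Bias is therefore possible, not certain. No sample-size figure in the documents is wrong on this account. The change should be made because the rule can produce a toxicity-linked omission and the remedy uses data already collected.

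**What to change.** Before the database lock:

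1. In SAP 4.3 and Protocol 10.2, replace the cut for safety analyses with a statement such as: all observed safety data from the safety set, including data collected under Protocol 5.6.1 after stopping IMP or after withdrawal from the trial, enter the safety summaries and the treatment-emergent event counts for as long as consent for follow-up holds.
2. Define discontinuation of IMP separately from discontinuation from the trial, and use the two terms consistently.
3. State how Early Termination visit values enter summaries that otherwise use scheduled time points only, for example by mapping them to a scheduled visit or by including them in the worst-value and clinically-significant counts.
4. Flag records obtained after discontinuation in the listings.

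The cost is a few sentences and some programming, with no new data. The downside is that safety rates may look slightly less favourable.
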